## **Recruitment**

### ***Patient Participants: Determining Orientation/ Emergence from PTA***

If a potential participant meets eligibility criteria based on medical record review, our research staff will approach him/her on the inpatient rehabilitation unit to determine whether the patient is cognitively capable of providing consent by administering a measure of orientation/ emergence from PTA: the Galveston Orientation and Amnesia Test (GOAT), the Revised GOAT, the full version of the Orientation-Log (O-Log), or the non-verbal version of the O-Log (orientation scores are not entered as data, but used only to determine orientation.) It is the choice of each site which version to use while assessing orientation/ emergence from PTA. Alternating use of the scales in an individual patient is not acceptable, however.

Please note that administration of the orientation test(s) is also a procedure for consenting into the TBIMS. As typically enrollment for BRITE will occur immediately following enrollment for TBIMS, for purposes of subject burden, the orientation test will not be repeated prior to BRITE enrollment.

Study researchers will follow the same procedures as TBIMS to assess for orientation/ emergence from PTA as outlined below:

“With prospective tracking, emergence from PTA is defined as:

- 1) two consecutive GOAT scores of 76 or greater with no more than 2 full calendar days between assessments (Assessment 1 = Friday, Assessment 2 = Monday, two full days = Saturday, Sunday)
- 2) two consecutive scores of 11 or greater on the Revised GOAT with no more than 2 full calendar days between assessments (Assessment 1 = Friday, Assessment 2 = Monday, two full days = Saturday, Sunday)
- 3) two consecutive scores of 25 or greater on the Orientation-Log with no more than 2 full calendar days between assessments (Assessment 1 = Friday, Assessment 2 = Monday, two full days = Saturday, Sunday)
- 4) two consecutive scores of 8 or greater on the Non-Verbal version of the Orientation-Log with no more than 2 full calendar days between assessments (Assessment 1 = Friday, Assessment 2 = Monday, two full days = Saturday, Sunday), or
- 5) in the judgment of a qualified clinician (i.e., speech-language pathologist, physician, neuropsychologist), the person has cleared PTA but administration of an orientation test is not possible due to language functioning.

The day of clearance of PTA is the first day the person gets the first of 2 consecutive scores of 76 or greater on the GOAT, the first of 2 consecutive scores of 11 or greater on the Revised GOAT, the first of 2 consecutive scores of 25 or greater on the Orientation-Log, or the first of 2 consecutive scores of 8 or greater on the Non-Verbal version of the Orientation-Log.”

As per standard TBIMS procedure, if the patient is deemed oriented, the research staff will introduce the study using a talking points script, and if the potential participant is interested, provide him/her with a brochure and a consent form.

Research staff will initiate the informed consent process if a) the patient is deemed oriented per definition above, and b) the patient expresses interest in participating. Research staff will visit the patient on a subsequent day and re-administer the orientation test prior to consent if needed.

*Patient Unable to Provide Consent*

If the patient is not deemed oriented as per the outline above, the patient is unable at that time to provide informed consent. Research staff may administer the orientation test multiple times to determine capacity to consent.

If patient is unable to provide consent either due to aphasia, non-emergence from PTA, and/or being non-verbal:

1. Staff will determine if patient has a Legally Authorized Representative (LAR) who is willing and available to provide consent as a proxy for the patient:
  - a. If Yes: Staff may enroll the patient participant via proxy- go to #2 below;
  - b. If No: Staff will deem the patient ineligible due to not being able to provide consent/no proxy- stop here.
2. Staff will determine if patient has an individual who is willing and available to assist with both participation in the RTP (if randomized to that arm)\* AND the follow-up questionnaires\*\* for the foreseeable future. Specifically, the individual would need to be present for all potential RTP contacts and questionnaires. This individual does not need to be the same person that provided proxy consent:
  - a. If Yes: Staff may enroll the patient participant via proxy-stop here;
  - b. If No: Staff will consult with trained clinical staff to conclude whether it is more likely than not that the patient participant will be able to participate on his/her own within one month following discharge given nature and degree of severity of limitations:
    - i. If Yes: Staff may enroll the patient participant via proxy;\*\*\*
    - ii. If No: Staff will deem the patient ineligible due to inability to complete study procedures due to cognitive/verbal limitations AND not having a proxy to assist with study procedures.

\*If the proxy individual is not enrolled as a caregiver participant in the study, the TCM would only engage the proxy individual in resource facilitation and the needs assessment as it specifically pertains to the patient participant. The TCM will not conduct a caregiver needs assessment with the proxy or provide resources that pertain specifically to the proxy individual as they are not enrolled as a caregiver. If the TCM infers that the proxy individual would like to participate in the needs assessments/resource facilitation as it pertains to them (e.g., as the caregiver), the TCM would remind the proxy individual in a non-coercive manner of the opportunity to participate as a caregiver participant. This would require the completion of the informed consent process with the proxy individual as per study protocol.

\*\*In this scenario, the proxy individual would not complete the QOLIBRI as part of the post-discharge questionnaire. In addition, the individual would not complete the following items on the Form II: SWLS, GEN, GNHLTH, PHQ, GAD

\*\*\*Staff will withdraw the patient participant following randomization if the participant is deemed unable to participate due to limitations within the following timeframes:

1. The TCM will withdraw the patient participant one month following discharge if randomized to RTP arm of the study;
2. Blinded staff will withdraw the patient participant three months following discharge if randomized to RDP arm of the study;

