### *Caregiver Participants*

Caregiver participants will be those individuals who will have primary care giving responsibility following rehabilitation care discharge of patients with moderate to severe TBI. Caregivers may be recruited while the patient is in the hospital or by telephone if not available during hospitalization. Research staff may enroll more than one individual as a caregiver following subject enrollment should a different individual assume the role of caregiver at a later time point (e.g. mother pre-discharge, significant other 3 months post-discharge). Multiple caregiver participants may be enrolled at the same time to accommodate if the caregiver role is assumed by different individuals at different points in time during participation (e.g. mother is caregiver at 3- and 9-months post-discharge, significant other is caregiver at 6- and 12-months post-discharge). Research staff will assess who has primary caregiving responsibilities both at each questionnaire period and the RTP phase (if applicable), and engage accordingly the particular participant who most clearly fits the role of primary caregiver.

Each site will assign a patient participant's ID number to their respective caregivers. The caregiver participant will keep the same ID number if enrolled in the study. Research staff will record which caregiver completes each questionnaire if more than one caregiver participant is enrolled at any given time.

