The patient participant will be instructed to sign one copy each of the consent form and HIPAA authorization form. The subject will then be asked to return all the signed, completed forms to the study staff via a self-addressed, stamped envelope previously mailed with the forms. The informed consent acquired directly from the participant will render the LAR consent obsolete.

Research staff will send a copy of the signed consent form to the patient participant with a cover letter.

*Caregiver Participants*

Caregiver participants may be initially recruited by telephone or in person. If the caregiver is not local and/or able to come in readily, or approach in person is not feasible, we request permission to waive written consent and instead obtain oral consent via use of an oral information statement sheet. Research staff may send an information statement sheet along with a cover letter if the caregiver will be enrolled following the discharge of the patient participant. Research staff would review the information statement sheet with the potential participant, then request verbal consent if the individual is interested in participating. Otherwise

the informed consent process may take place in person and will take place during the participant's inpatient rehabilitation stay with our research staff. Caregivers will provide written consent if enrolled in person.

All participants approached for possible enrollment in this study will be clearly informed that if they choose not to participate in this project, they and/or their loved one will still be able to receive any of the routine medical and rehabilitation services available to them.

They will be informed that their participation is voluntary and that they may withdraw their consent and discontinue participation in the study at any time. Any new information developed during the course of the study that might affect a participant's understanding of the research and willingness to continue to participate will be brought to their attention by study staff.

The caregiver participant may be given a response key to assist with completing the questionnaires described in the "Follow Up Data Collection" section below. The response key may be given in person following consent, or mailed at a separate time with a cover letter.

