**Randomization/ Post-Discharge Transition Phase**

After the patient participant has been discharged or after they are consented post-discharge, s/he will be randomly assigned 1:1 into one of two study arms: RDP or RTP. We will stratify randomization on study site and discharge destination (another facility vs. home/ community):

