#### Caregiver Withdrawal

Caregivers may withdraw from the study independently from participants. The principles are the same as to encouraging the caregiver to remain involved for data collection. A caregiver participant will remain enrolled in the study and kept on the schedule for data collection even if the respective patient participant withdraws from the study unless the caregiver participant explicitly states s/he wishes to withdraw as well.

Also, after discussion with both the patient and caregiver participant, a caregiver participant may be discontinued if another individual has become the clear caregiver. For instance, the caregiver participant at the time of discharge could be the mother, but then the patient's significant other is the true caregiver at the time of the 3-month questionnaire.

In this scenario, the mother should be discontinued, and the significant other should be enrolled as the new caregiver participant.

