**Aim 1, Hypothesis 1:** Both the PART-O-17 and the QoLIBRI measures are numeric with a fairly large range that can be considered as continuous for data analysis. We will test the difference in means for PART-O-17 and QoLIBRI between the two groups at 6-month post-discharge using a two-sided t-test for independent samples. We will also test if the intervention has a long-term effect by comparing the two groups at 12-months post discharge using the same type of t-test.

**Aim 2, Hypothesis 2:** To compare the trajectory of improvement for 3-, 6-, 9- and 12-months post-discharge, we will plot individual trajectories over time and if it appears that the majority of people are leveling off over time we will consider a growth model. Otherwise, we will use a linear mixed model, with the outcome (PART-O-17 or QoLIBRI) as the response variable, and time and other factors (such as age, sex, race/ ethnicity, education, injury severity) as explanatory variables, and add intervention group and its interaction with time to test whether the interventions and time had an effect in the trajectory of the outcome.

**Aim 3, Hypothesis 3:** To compare the healthcare utilization in the first-year post discharge, the two groups will be compared on the distribution of categories of completed planned outpatients visits (less than 50%, between 50 and 75%, and more than 75%) by using a Chi-Square test. Both, the number of urgent care visits and the number of unplanned hospitalizations will be compared by means of a Poisson regression, which will include group and possibly adjusting for other factors (age, sex, race/ethnicity, education, injury severity). A statistically significant coefficient for intervention groups will show that the two groups differ in emergency and unplanned medical visits.

**Aim 4, Hypothesis 4a:** To compare caregiver burden, HRQOL, and satisfaction with roles and activities, we will apply t-tests for difference of means for independent samples for those measures that are found to have a normal distribution. We will also conduct heterogeneity of treatment effects analyses as we planned for other measures.

**Aim 4, Hypothesis 4b:** Using the Bakas Caregiving Outcomes Scale, Zarit Burden Interview, Sf-12, and the PROMIS Satisfaction with Social Roles and Activities for caregivers at 3-, 6-, 9- and 12-month follow-ups as response variables, we will fit a linear mixed model or growth model similar to the ones in hypothesis 2.

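### Aim 4 analyses all enrolled caregivers, including those who join after the arm is known, and RTP has an added route for such enrolment, so the caregiver sample can be partly arm-dependent

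*Combined protocol and SAP*

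**What the plan says.** **When the arm is assigned.** Under Randomization/ Post-Discharge Transition Phase, the patient is the randomised unit. Once the patient has left hospital, or has consented after leaving, "s/he will be randomly assigned 1:1 into one of two study arms". The TBI Care Manager (TCM) then writes to the patient and any caregiver, and the letter differs by arm. Under Masking, coordinators and TCMs know the assignment.

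**When caregivers enrol.** Under Recruitment, Caregiver Participants: "Caregivers may be recruited while the patient is in the hospital or by telephone if not available during hospitalization". The same section adds that "Research staff may enroll more than one individual as a caregiver following subject enrollment", with a significant other at 3 months after discharge as an example. The Consent section provides an information sheet "if the caregiver will be enrolled following the discharge of the patient participant". Under Caregiver Withdrawal, if another person has become the true caregiver by the 3-month questionnaire, "the mother should be discontinued, and the significant other should be enrolled as the new caregiver participant". No section requires caregiver consent before randomisation.

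**What RTP adds.** A footnote under Patient Unable to Provide Consent concerns proxies who are not enrolled as caregivers: "The TCM will not conduct a caregiver needs assessment with the proxy or provide resources that pertain specifically to the proxy individual". If the TCM infers that the proxy would like such help, "the TCM would remind the proxy individual in a non-coercive manner of the opportunity to participate as a caregiver participant".

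**What is analysed.** For Hypothesis 4a, "we will apply t-tests for difference of means for independent samples". Hypothesis 4b uses mixed or growth models. The intention-to-treat statement covers randomised cases and gives no rule for caregivers who join late or are replaced. Caregiver baseline data are relationship and demographics only.

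**The concern.** Randomising patients protects a comparison of caregivers only if membership of the caregiver sample is settled before the arm can influence it. Here it need not be. After assignment, a proxy in RTP may be reminded that enrolment is open and receives help for themselves only by enrolling. RDP has no scheduled TCM contacts, so it has neither the reminder nor that inducement. The trigger is a perceived wish for caregiver help, which is plausibly related to what the Bakas Caregiving Outcomes Scale (BCOS) and the Zarit interview measure.

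The RTP and RDP caregivers could therefore differ in who is measured as well as in what was delivered. The planned t-test cannot separate the two. Because no caregiver outcome is taken at baseline, the imbalance cannot be properly checked or adjusted for later. At stake is the reading of Hypotheses 4a and 4b.

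**Working it through.** **1. The plan's own figure.** Power for Secondary Outcomes gives SD 13, a BCOS change from 56 to 59 (3 points, effect size 0.23), two-sided α 0.05, and power 0.76 with 540 caregivers. Check: SE = 13 × √(4/540) = 1.119; 3/1.119 = 2.681; Φ(2.681 − 1.960) = 0.765. The figure reproduces, so the issue is who is in the sample, not the arithmetic.

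**2. Caregivers expected at 6 months.** The Milestone Schedule gives 432. SE = 13 × √(4/432) = 1.251; 3/1.251 = 2.398; power = Φ(0.438) = 0.67. The detectable difference at 80% power is 2.80 × √(4/432) = 0.27 SD, or 3.5 points.

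**3. Size of a selection bias (assumed inputs).** The documents give neither the share of RTP caregivers who enrolled because of the arm nor how they differ. With share *s* and mean difference *d*, bias = *s* × *d*.

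- Low end: 0.05 × 0.3 SD = 0.015 SD; × 13 = 0.2 points.
- High end: 0.20 × 0.5 SD = 0.10 SD; × 13 = 1.3 points.

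**4. Effect on the test.** This uses 432 caregivers and *d* = 0.5 SD = 6.5 points, with the extra caregivers in RTP only (normal approximation). The last column assumes a true 3-point benefit and late RTP caregivers who are worse off.

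| Share *s* | Bias (points) | % of 3-point target | Two-sided type I error | Power |
|---|---|---|---|---|
| 0 | 0 | 0 | 0.050 | 0.67 |
| 5% | 0.33 | 11 | 0.058 | 0.57 |
| 10% | 0.65 | 22 | 0.081 | 0.47 |
| 20% | 1.3 | 43 | 0.178 | 0.27 |

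A higher BCOS is better in the plan's calculation, so more burdened late RTP caregivers lower the RTP mean.

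**5. Precision lost by restricting to caregivers consented before randomisation (432 assessed; excluded share assumed).**

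- 5% excluded (410 left): 2.80 × √(4/410) = 0.28 SD, or 3.6 points.
- 15% excluded (367 left): 2.80 × √(4/367) = 0.29 SD, or 3.8 points.
- 10%, 20% or 30% excluded (389, 346 or 302 left): power for 3 points is 0.62, 0.57 or 0.52.

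**The case against.** The reminder is narrow. It sits in a footnote on patients who cannot consent, applies only to a proxy not already enrolled, and only when the TCM infers interest. The proxy must also meet the caregiver criteria. In the table's 20% row, with 192 RDP and 240 RTP caregivers, about 48 people (0.20 × 240) would have to enter through it, which is a lot for one footnote.

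Ordinary late enrolment is open to both arms: staff ask who the primary caregiver is at each questionnaire, and replacement is not tied to arm. Aim 4 is secondary, and the plan says non-primary results will be read with caution.

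A reader might infer that Aim 4 does not compare randomised groups at all, or that RTP runs a general caregiver recruitment channel that RDP lacks. The documents support neither. Caregivers can consent in hospital, before randomisation, and for them entry to the sample cannot depend on the arm. What RTP alone has is the reminder, the tie between enrolment and caregiver help, and one further occasion (the RTP phase) for identifying the primary caregiver.

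The restriction also has a cost to relevance. It drops caregivers who could not be reached during the stay and those who hold the role at 6 months after a change, in a trial meant to be pragmatic.

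All of this stands as a limit on size and on wording. It does not remove the gap: the plan admits arm-influenced entry, sets no rule for it, and has no baseline measure with which to examine it. Caution in interpretation is no substitute, because without enrolment by arm and timing a reader cannot judge the extent.

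**Conclusion.** The point holds in a limited form. As written, Aim 4 includes caregivers who enrol after the arm is known, and RTP has an added route for them, so the sample can be partly arm-dependent. The documents do not give the share or the direction. The bias of 0.2–1.3 BCOS points against a 3-point target rests wholly on the assumed 5–20% share and 0.3–0.5 SD difference, and is an illustration.

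A reader might infer that the bias favours RTP. The text does not support that: if the late RTP caregivers are more burdened, which is plausible given the trigger, the bias would hide a benefit. Caregivers who consented before randomisation remain a randomised comparison, subject to later dropout. The patient outcomes in Aim 1 are unaffected.

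**What to change.** Add to the Aim 4 analysis plan, before caregiver outcomes are examined by arm (if they already have been, label the analysis post hoc):

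1. An analysis restricted to caregivers who consented before the patient's randomisation, alongside the all-caregiver analysis. If the two differ materially, base the causal conclusion on the restricted set.
2. Caregiver enrolment and replacement reported by arm and by before or after randomisation, for example in the caregiver part of the CONSORT diagram.
3. Confirmation that caregiver consent dates and randomisation dates can be retrieved. The documents say the assignment is recorded automatically, but do not say that a caregiver consent date is held in the database.

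The milestone schedule puts the end of recruitment at 10/31/2021, so only the analysis can change. The cost is analysis work and precision. With 432 assessed, the detectable difference rises from 0.27 to 0.28–0.29 SD if 5–15% are excluded. Ordinary late and replacement caregivers in both arms also leave the set, so the loss could be larger: at 10–30% excluded, power for 3 points falls from 0.67 to 0.62–0.52. Keeping the all-caregiver analysis beside it preserves the pragmatic reading. If few caregivers enrolled late, the two will nearly coincide, and the report will show it.
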